8.1.3 Visit 3-8

These visits must be scheduled 28 days after the previous visit with a visit window of 3 days, except visit 3 that must be scheduled 14 days after visit 2. The main reasons for these visits are to assess the patient's medical status after a longer use of the trial product.

At visit 5 some extra safety assessment will be performed, see the flow chart in section [2](#).

The assessments to be performed at these visits are listed in section [2](#).

Key reminders:

- Ask if the patient has experienced any AEs since last visit
- Ask for any concomitant medications since last visit
- Dispensing session for trial product until next visit must be performed in the IWRS
- Drug accountability of trial product must be recorded in the IWRS
- Collect and review of the diary
 - Evaluate together with the patient the correctness of the haemostatic efficacy for treatment of bleeds
- Check for 48 hours washout of trial product before the inhibitor test
- Trial product must be dispensed
- Next visit should be scheduled

8.1.4 Visit 9 and visit 10 (Dispensing visits) – extension phase

The dispensing visits in the extension phase must be scheduled 56 days (approximately 2 months) after the previous visit with a window of 2 weeks. The main reason for these visits is to dispense trial product to the patient or parent/caregiver. In case the patient has a positive inhibitor (≥ 0.6 BU) some laboratory test must also be performed, see section [2](#).

Visit 9 and 10 will be repeated every six months until LPLV with a consecutive visit number see section [7](#).

The assessments to be performed at these visits are listed in section [2](#).

Key reminders:

- Ask if the patient has experienced any AEs since last visit
- Ask for any concomitant medications since last visit
- Dispensing session for trial product until next visit must be performed in the IWRS
- Drug accountability of trial product must be recorded in the IWRS
- Review of the diary
 - Evaluate together with the patient the correctness of the haemostatic efficacy for treatment of bleeds

- Trial product must be dispensed
- Next visit should be scheduled

8.1.5 Visit 11 (Assessment visits) extension phase

The assessment visits in the extension phase must be scheduled 56 days (approximately 2 months) after the previous dispensing visit with a window of 2 weeks. The main reasons for these visits are to assess the patient's medical status after a longer use of the trial product.

Visit 11 will be repeated every six months until LPLV with a consecutive visit number see section [7](#).

The assessments to be performed at this visit are listed in section [2](#).

Key reminders:

- Ask if the patient has experienced any AEs since last visit
- Ask for any concomitant medications since last visit
- Dispensing session for trial product until next visit must be performed in the IWRS
- Drug accountability of trial product must be recorded in the IWRS
- Collect and review of the diary
 - Evaluate together with the patient the correctness of the haemostatic efficacy for treatment of bleeds
- Check for 48 hours washout of trial product before the inhibitor test
- Trial product must be dispensed
- Next visit should be scheduled

8.1.6 Surgery visits - main and extension phase

Patients undergoing surgery will continue the regular visit schedule and will not need to reschedule visits during the surgery period, except if the surgery treatments do not allow for the necessary washout period of 48 hours, then the visit must be re-scheduled.

The surgery and the injection of trial product during the surgery and in the post-operative period will be recorded in the eCRF, except if the injection is performed at home or at another site as these doses will be recorded in the diary and then later transferred into the eCRF by the trial site. For more information regarding surgery see section [8.3.5](#). The post-operative period is defined as the period the patient is not following his ordinary planned treatment regimen after the surgery has been performed.

The assessments to be performed at this visit are listed in section [2](#).

Key reminders:

- Ask if the patient has experienced any AEs since last visit
- Ask for any concomitant medications since last visit
- Dispensing session for trial product during surgery must be performed in the IWRS
- Before the surgery day the patient must have a negative inhibitor test and a satisfactory recovery test from central laboratory, except for emergency surgery, see section [8.3.5](#)
- Evaluate if a PK is necessary especially before a major surgery.

8.1.7 Unscheduled visits - main and extension phase

An unscheduled visit can be performed after the screening visit has been performed. Unscheduled visits can also be performed at the surgery day and during the post-operative surgery period. The date and time of the unscheduled visits must be recorded in the eCRF.

The main reason for the unscheduled visits is to record information that is important for this trial that do not occur during the scheduled visits. This information can be laboratory tests, dosing adjustments, a dose injection or for determination of half-life in case the patient has a low titer inhibitor (≥ 0.6 BU and ≤ 5 BU), lab samples to confirm a positive inhibitor test or a PK before surgery. Please note that AEs, withdrawal criteria and concomitant medication must be assessed at every unscheduled visit. Phone calls should not be recorded as an unscheduled visit as the patient have not visited the trial site, but information regarding the call must be recorded in the medical records.

Unscheduled visits can be performed to dispense additional trial product during the day of surgery and the post-operative period.

The assessments that can be performed at this visit are listed in section [2](#).

Key reminders:

- Ask if the patient has experienced any AEs since last visit
- Ask for any concomitant medications since last visit
- Check for 48 hours washout of trial product before a possible inhibitor test

8.1.8 End of trial visit - main and extension phase

For patients who withdraw from the trial, an end of trial visit must be performed as soon as possible. For the main phase, visit 8 is the end of trial visit. If the patient will not continue into the extension phase then visit 8 will be the last visit and the end of trial form must be filled in at this visit.

The assessments to be performed at this visit are listed in section [2](#).

Key reminders:

- Ask if the patient has experienced any AEs since last visit
- Ask for any concomitant medications since last visit
- Check for 48 hours washout of trial product before the inhibitor test
- Completion or withdrawal session must be performed in the IWRS

8.1.9 Follow up visit

Patients withdrawn due to inhibitors must attend a follow up visit 3 times with a month apart for a follow up of the patient's inhibitor status. The first follow up visit should be 28 days after the end of trial visit with a visit window of 2 weeks and the next follow up visits should likewise be after 28 days with a window of 2 weeks.

The lab tests to be performed at this visit are listed in section [2](#).

Key reminders:

- Ask if the patient has experienced any AEs since last visit
- Check for 48 hours washout of FVIII products before the inhibitor test

8.2 Patient related information

8.2.1 Concomitant illness and medical history

A **concomitant illness** is any illness that is present at the start of the trial (i.e. at the first visit, screening visit).

Medical history is a medical event that the patient has experienced in the past. Historical bleeding episodes should not be recorded in medical history as this will be collected in another eCRF form called "Haemophilia treatment and bleeding history".

The information collected for concomitant illness and medical history should include diagnosis, date of onset and date of resolution or continuing, as applicable.

Any change to a concomitant illness should be recorded during the trial. A clinically significant worsening of a concomitant illness must be reported as an AE.

8.2.2 Concomitant medication

A **concomitant medication** is any medication, other than the trial products, which is taken during the trial, including the screening period.

Details of any concomitant medication must be recorded at the first visit. Changes in concomitant medication must be recorded at each visit as they occur.

The information collected for each concomitant medication includes trade name or generic name, indication, start date and stop date or continuing.

If a change is due to an AE, then this must be reported according to section [11](#). If the change influences the patient's eligibility to continue in the trial, the monitor must be informed.

The following concomitant medications are not allowed from visit 2 and during the course of this trial:

- Vitamin K antagonists
- Direct thrombin inhibitors
- Direct factor Xa inhibitors
- FVIII concentrates (other than turoctocog alfa)
- Coagulation factor containing products including PCC, aPCC, whole blood, plasma or cryoprecipitate are allowed in emergency situations for a maximum of 5 administrations. Unrestricted uses of factor containing products is allowed during surgery. See [Table 8-1](#) for washout periods and section [8.5.3.1](#) and [8.5.3.2](#) for necessary laboratory tests
- Use of heparin for a period exceeding 1 month, except for flushing of CVAD

8.2.3 Haemophilia treatment and bleed history

Historical information regarding the patient's previous haemophilia A treatment and bleeding pattern must be recorded at visit 1.

Going back 1 year. In case a child is younger than 1 year then until date of birth.

- Type of treatment regimen (on-demand, prophylaxis, treatment of bleed)
- Start date of regimen
- Stop date of regimen
- Number of bleeds during regimen period (per year)
- Type of product during regimen period
- Dose
- Dosing frequency

From birth:

- Total number of previous exposure days (≥ 50 ED, ≥ 100 ED or exact number of ED).

The "total number of previous exposure days" must be assessed to ensure that an inclusion criteria is met, see section [6.2](#). The previous exposure days must be documented in medical records, which may be calculated based on known treatment regimen(s).

8.2.4 Haemophilia details

Historical information regarding the patient's haemophilia A status must be recorded at visit 1.

- Date of diagnosis of haemophilia A
- Inhibitor tests taken (yes/no)
- Cut off value for positive inhibitor result

8.2.5 Body measurements

Body weight can be measured at visit 1, visit 5 and visit 8 in the main part of the trial. In the extension part it can be measured at every assessment and dispensing visit. See [Table 8–2](#) and [Table 8–3](#) for when it is mandatory.

If necessary height and weight can also be measured at an unscheduled visit.

- Body weight (kg) [xxx.x]
- Height (cm) [xxx.x]

Table 8–2 Body measurements – main trial

Age	Weight AND height	Weight OR height
0-5 years	Visit 1, 5 and 8	
>5 < 18 years	Visit 1 and 8	Visit 5 (only height)
18 years plus	Visit 1	Visit 8 (only weight)

Table 8–3 Body measurements – extension part

Age	Weight and height	Only weight
0-5 years	Visit 11, 14, 17 and 20	Visit 9, 10, 12, 13, 15, 16, 18 and 19
>5 < 18 years	Visit 11, 14, 17 and 20	
18 years plus		Visit 11, 14, 17 and 20

8.2.6 Demography

Following information will be collected at visit 1.

- Date of birth
- Sex
- Race

The patient's "Sex" and "Race" must be used for the assessment of inclusion criteria, see section [6.2](#)

8.3 Assessments for efficacy

To ensure standardisation of methods across the trial sites, definitions for evaluation of bleeding episodes, such as the haemostatic evaluation, are provided in this protocol.

All assessments used in this trial are widely used and are standard assessments used for care of haemophilia A patients.

8.3.1 Bleeding episodes

During the entire trial period all bleeding episodes treated with turoctocog alfa or another haemostatic medication must be entered in the diary, see section [8.6.2](#). Bleeding episodes which do not require treatment can also be entered in the diary

The following will be recorded in the diary for bleeding episodes:

- Date and time of start of bleed
- Date and time of stop of bleed, see [Table 8-4](#)
- Anatomical location of the bleeding episode (Joint, muscle, skin, stomach (gastrointestinal bleeding), mucosal (mouth, gums, nose), urinary system, central nervous system, other)
 - If joint is chosen: knee, ankle, wrist, fingers, elbow, shoulder, hip, toes, jaw
 - If muscle or skin is chosen: arm, leg, hand, buttocks, head/neck, chest, back, stomach, foot
- Anatomical position of body part (left, right)
- Classification of bleed (spontaneous, traumatic, surgical)
- Severity category (mild/moderate or severe), see [Table 8-6](#) Only evaluated by site
- Haemostatic treatment (turoctocog alfa or other treatment to achieve haemostasis)
- Non-medical therapy used
- Clinical evaluation of the haemostasis (Excellent, Good, Moderate or None) – only for bleeds treated with turoctocog alfa, see [Table 8-5](#)

Table 8-4 Definition of stop of bleed

Stop time is:
When the patient/parent or LAR experiences/observes signs of cessation of the active bleed such as; pain relief, no increase in swelling/limitation of motion and improvement in other objective signs of the bleeding episode
Stop time is not:
When pain and objective signs of the bleeding episode are completely resolved

Table 8–5 Definition of haemostatic response

Category	Definition
Excellent	abrupt pain relief and/or unequivocal improvement in objective signs of bleeding within approximately 8 hours after a single injection
Good	definite pain relief and/or improvement in signs of bleeding within approximately 8 hours after an injection, but possibly requiring more than one injection for complete resolution
Moderate	probable or slight beneficial effect within approximately 8 hours after the first injection; usually requiring more than one injection
None	no improvement, or worsening of symptoms within approximately 8 hours after the first injection; usually requiring more than one injection

The patient or parent/caregiver must in the diary assess the haemostatic efficacy for treatment of bleeds, but the investigator must together with the patient during the diary review evaluate the correctness of the evaluation.

Table 8–6 Definition of bleeding episode severity

Category	Definition	Comment
Mild/Moderate	Minor bleeds which are uncomplicated joint bleeds, muscular bleeds without compartment syndrome, mucosal or subcutaneous bleeds	
Severe	Major bleeds that require hospitalisation; intracranial, retroperitoneal, iliopsoas and internal neck bleeds; muscle bleeds with compartment syndrome; bleeds associated with a significant decrease in the haemoglobin level (>3g/dl). Traumatic bleeds at other locations than described above can always be considered severe at the investigators discretion.	These bleeding episodes must be treated immediately at home or at the local emergency room, and the trial site must be contacted..

Table 8–7 Definition of bleeding episode categorisation

Category	Comment
Spontaneous	Not linked to a specific event
Traumatic	Caused by a specific, known action or event (e.g. injury or exercise)
Surgical bleed	Bleeds after surgery from the surgical wound. Bleeding episodes during surgery does not fall under this category and will be evaluated in the surgical haemostatic evaluation
Re-bleed	Classification will be done by Novo Nordisk as part of the statistical analysis based on bleeding information: Re-bleed is defined as a bleed (worsening of bleeding site conditions e.g. swelling, pain) within 72 hours after stopping of a previous bleed at the same (or subset of the same) anatomical location. If a bleed occurs in the same location 72 hours after stopping, the treatment is defined as a new bleeding episode

8.3.2 Injection of trial product

The following information will be recorded regarding the injection of trial product:

Actual dose:

- Dose (volume and vial strength)
- Start date and time of injection
- Stop date and time of injection (only for PK)
- Reason for dosing (prophylactic, treatment of bleeding episode , surgery, PK or other)
- Injection method (butterfly or other)

Planned regimen and dosing:

- Planned regimen (prophylaxis, on-demand)
- If the regimen is prophylaxis:
 - Dosing frequency
 - Planned dose (mL, IU/kg and vial strength)
- Did you use butterfly (without flushing) for injection (yes/no)

See section [5.3](#) for an overview of the requirements and guidelines for dosing and dose frequency.

8.3.3 Target joint assessments

A target joint is defined as 3 or more bleeds in the same joint within 6 months. When there has been no bleed in the same joint for 12 months, such a joint is no longer considered a target joint.

The following will be recorded in the eCRF:

- Anatomical location of target joint (knee, ankle, wrist, fingers, elbow, shoulder, hip, toes, jaw)
- Anatomical position of target joint (left, right)
- Number of bleeds in target joint within the last 12 months (only at visit 1)

Target joint assessment will be performed at visit 1 and visit 8 in the main phase of the trial and at the assessment and end of trial visit in the extension part of the trial.

8.3.4 Pharmacokinetics

PK at visit 2 will take 48 hours for patients who are 12 years and older and will take 24 hours for children below the age of 12 years, see [Table 2–2](#) for the specific sampling time points. Only the pre-dose sample can be taken with other samples if they have to be performed before dosing. This PK can also be performed for surgery patients. The patients that perform a PK at visit 2 must also perform a recovery test at visit 8 (see [8.5.2.3](#)) with the same dose as at visit 2.

A determination of the half-life by sampling at different time points will be performed at an unscheduled visit for patients that have a low titer inhibitor (≥ 0.6 BU and ≤ 5 BU) see section [8.4.2.1](#).

CRP must be sampled before dosing for PK, see section [8.5.2.2](#), to ensure accurate interpretation of PK results (e.g. in case measurements are affected by inflammation or infection).

The vein used for injection of trial product must not be used for blood sampling until more than 30 minutes after the injection, i.e., cannot be used for the 30 minutes post-dose sample.

The PK sampling should be rescheduled if any of the following applies:

- Major surgery performed 1 month prior to PK
- Use of FVIII product prior to PK, see [Table 8–1](#) for the age dependent washout periods
- Illness or fever 48 hours prior to PK
- In a bleeding state that requires treatment with haemostatic agent

If a treatment-requiring bleeding episode interferes with PK sampling and assessments, rescheduling of PK sessions can be done at the discretion of the investigator taking the patient's safety and the bleeding episode severity into account.

The PK dose is 50 ± 5 IU/kg BW of trial product and the lines/tubes must be flushed immediately, with 2-5ml sodium chloride, after administration of the trial product.

The injection stop time of the PK dose is time 0.

FVIII activity will be analysed by using a chromogenic and a one stage FVIII clotting assay and both assays are validated.

The remainder of the PK sample will, after the initial analysis, be used for further research. A separate informed consent will be requested for this. See further information in section [8.5.3.6](#) and [8.5.3.7](#) for handling of the stored samples

A final draft bio-analytical report from the laboratory for PK analyses must be available at database lock to Novo Nordisk.

The parameters that will be calculated using the PK sampling at visit 2 is shown in [Table 8-8](#).

Table 8-8 Definition of PK parameters

Parameter	Description	Calculation
$t_{1/2}$ (hours)	Terminal half-life	$t_{1/2} = \ln(2) / \lambda_z$, where λ_z is the terminal elimination rate. The terminal elimination rate will be estimated using linear regression on the terminal part of the time vs. log(concentration) curve
AUC_{last} ((IU*h)/mL)	Area under the plasma concentration vs. time curve from time zero to the last measurable concentration	AUC_{last} is calculated using the linear trapezoidal method from time 0 to the time for the last measurable concentration. The concentration at time 0 will be estimated by log-linear extrapolation of the two initial post-administration concentrations (see below) and used in the calculation of AUC_{last} .
Incremental Recovery ((IU/mL)/(IU/kg))	Peak level recorded 30 min. after end of infusion, adjusted for pre-administration concentration ([IU/mL]/[IU/kg])	The incremental recovery is calculated as (FVIII:C activity measured in plasma 30 min after dosing - FVIII:C activity measured in plasma immediately before dosing) / (dose injected at time 0 min), where the dose is expressed as IU FVIII product per kg BW.
AUC_{0-inf}	Area under the concentration vs. time from time curve zero to infinity	$AUC_{0-inf} = AUC_{last} + (C_{(t)} / \lambda_z)$, where $C_{(t)}$ is the last measurable concentration.
AUC%Extrap	The extrapolated part of AUC_{0-inf}	$100 \cdot (C_{(t)} / \lambda_z) / AUC_{0-inf}$. This is not a PK parameter. It is only a description of the extent of extrapolation in the AUC calculation.
C_{max} (IU/mL)	The maximal concentration	The maximal observed concentration. Note that this will likely be obtained at the first measurement and will be sensitive to deviations from the scheduled sampling time. This limits the value of this parameter, especially when comparing to other studies.
CL (mL/h/kg)	Total plasma clearance of drug after intravenous administration	$CL = \text{Dose} / AUC_{0-inf}$

Parameter	Description	Calculation
MRT (hours)	Mean Residence Time	$MRT = AUMC/AUC_{0-inf}$, where AUMC is the area under the first moment curve, i.e. the area under the curve $t \cdot C(t)$, calculated with the same method as AUC (linear trapezoidal method + extrapolated area).
V_{ss}	Apparent volume of distribution at equilibrium	$V_{ss} = CL \cdot MRT$
V_z	Apparent volume of distribution based on the terminal phase	$V_z = CL/\lambda_z$
$C_{(0)}$	The estimated concentration at time 0 (end of infusion), given that the dose was given as an instantaneous bolus.	$C_{(0)}$ will be calculated by log-linear extrapolation of the two initial post-administration concentrations. If the second value is not lower than the first value, $C_{(0)}$ will be defined as the highest of these two.

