5.3.4 Treatment of bleeding episodes

Bleeds occurring during both the on-demand and in the prophylaxis treatment regimen will be treated with one or more turoctocog alfa i.v. bolus injections. The individual dose is determined by the investigator, using the recommendations in the World Federation of Haemophilia (WFH) guidelines¹⁰.

Dose (IU) = weight (kg) x desired factor level (IU/dl) x 0.5

Example: 50kg x 40IU/dl x 0.5 = 1000 IU of turoctocog alfa

In case of bleeding events, [Table 5-2](#) as well as the WFH guideline¹⁰ may be used to guide dosing. FVIII activity should not fall below the lower range for the given plasma activity level (in % of normal or IU/dl) until the bleeding episode is resolved. As the guidelines are recommendations non-compliance with them will not require protocol deviations. The maximum dose per injection mentioned in this protocol must though be followed.

Table 5–2 Guide for trial product dosing in bleeding episodes¹

Degree of haemorrhage	FVIII level required (%)(IU/dl)	Frequency of doses (hours)/ Duration of therapy (days)
Early haemarthrosis, muscle bleeding or oral bleeding	20-40	Repeat every 12 to 24 hours until the bleeding episode as indicated by pain is resolved or healing achieved
More extensive haemarthrosis, muscle bleeding or haematoma	30-60	Repeat injection every 12 to 24 hours for 3-4 days or more until pain and acute disability are resolved
Life-threatening haemorrhages	60-100	Repeat injection every 8 to 24 hours until threat is resolved

X¹ NovoEight[®] approved summary of turoctocog alfa characteristics

This formula may be used to calculate resulting factor levels:

$IU/dl \text{ (or \% of normal)} = [Total \text{ Dose (IU)}/BW \text{ (kg)}] \times 2 [IU/dl]/[IU/kg]$

Example: $2000 \text{ IU} \times ([2 \text{ IU/dl}]/[IU/kg]) / 70 \text{ kg} = 57 \text{ IU/dl}$

A dose of 2000 IU administered to a 70 kg patient should result in a post-injection FVIII level increase of 57 IU/dl, or 57%.

The patient will be withdrawn from the trial in case he is treated with another FVIII product than turoctocog alfa, see section [6.4](#)

Bleeding treatment should start as soon as a bleed is identified. The investigator should provide the patient in advance the doses needed to treat the bleed of different severities.

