6.2 Inclusion criteria

For an eligible patient, all inclusion criteria must be answered “yes”.

1. Informed consent obtained before any trial-related activities. Trial-related activities are any procedures that are carried out as part of the trial, including activities to determine suitability for the trial
2. Male patients
3. Age from 0 years
4. Severe congenital haemophilia A (FVIII \leq 1%)
5. History of exposure days (ED) to any FVIII concentrates fulfilling the criteria of previously treated patients:
5a: Patients of 12 years or above: 100 exposures days (ED) or more
5b: Patients below 12 years: 50 exposure days (ED) or more
6. Asian ethnicity and resident in China

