- Next visit should be scheduled

8.1.2.1 PK at visit 2

Blood sampling for PK will be performed during a period of 48 hours for patients who are 12 years and older and 24 hours for children below the age of 12 years, see [Table 2-2](#) for the specific sampling time points. It is not required that the patient stay overnight.

PK sampling must start after the assessments performed at visit 2. See section [8.3.4](#) for more information in regards to the PK sampling.

Patients must not be dosed with FVIII or other products containing FVIII before the PK session, see [Table 8-1](#) for the required washout periods as this is dependent of the age.

Key reminders:

- Check for adequate washout periods of FVIII products before the trial product injection, see [Table 8-1](#) and for other rescheduling criteria, see section [8.3.4](#)
- PK dose is 50 ±5 IU/kg BW

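### Table 8-8 subtracts pre-dose FVIII for incremental recovery but not for AUC, clearance or half-life, so any endogenous activity biases those three endpoints

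*Protocol*

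**What the plan says.** Protocol section 8.3.4, Table 8-8, treats pre-dose activity in two ways.

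- Incremental recovery is the 30-minute level "adjusted for pre-administration concentration": the pre-dose value is subtracted.
- For half-life, "The terminal elimination rate will be estimated using linear regression on the terminal part of the time vs. log(concentration) curve". No baseline term appears.
- AUC to the last measurable concentration "is calculated using the linear trapezoidal method from time 0 to the time for the last measurable concentration". AUC0-inf adds the last concentration divided by the terminal rate, and clearance is dose divided by AUC0-inf. Neither has a baseline term. MRT, Vss and Vz inherit this.

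Inclusion criterion 4 (section 6.2) requires "Severe congenital haemophilia A", defined as FVIII of 1% or less, so an endogenous level up to and including 1 IU/dl is allowed. Table 2-2 draws a pre-dose sample in every profile, and section 8.5.2.3 requires a baseline FVIII level at visit 1.

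The SAP repeats the PK endpoints under Pharmacokinetic endpoints, adds no correction, and in section 3 declares no changes to the protocol analyses.

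Protocol section 8.5.2.3 also defines incremental recovery, as the 30-minute activity divided by the dose, without subtracting the pre-dose value. This differs from Table 8-8.

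**The concern.** Endogenous FVIII is constant over the sampling period, while the injected drug falls. On a log scale a small constant hardly matters near the peak but matters at 48 h, and the late samples set the terminal slope. A flatter slope lengthens the estimated half-life. The constant also adds area under the curve, including the extrapolated part, so clearance falls.

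The table corrects the parameter that needs it least. At 1 IU/dl, leaving recovery uncorrected would shift it by about 1%, whereas half-life can shift by much more.

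Half-life, AUC0-inf and clearance are named endpoints, and the PK session exists to characterise turoctocog alfa in a Chinese population. Only 12 to 18 patients contribute, so a few affected profiles could move a geometric mean.

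**Working it through.** The documents give no expected half-life or clearance to reproduce. The check is to apply Table 8-8 as written to a known profile and see what it returns.

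**Inputs from the documents**
- Dose: "The PK dose is 50 ± 5 IU/kg BW of trial product" (section 8.3.4).
- Peak: section 5.3.4 uses 2 IU/dl per IU/kg. Its example is 2000 x 2 / 70 = 57.1 IU/dl, agreeing with the statement that the dose "should result in a post-injection FVIII level increase of 57 IU/dl, or 57"%. So 50 IU/kg gives 50 x 2 = 100 IU/dl.
- Endogenous level B: at most 1 IU/dl (section 6.2); 0.2 and 0.5 were also tried.
- Schedule: "Blood sampling for PK will be performed during a period of 48 hours for patients who are 12 years and older and 24 hours" below 12 (section 8.1.2.1). Table 2-2 gives post-dose times of 0.25, 0.5, 1, 4, 8, 12, 24, 30 and 48 h from age 12, and 0.5, 4 and 24 h below 12.

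**Assumptions not in the documents**
- True half-life T of 8, 10 or 12 h with mono-exponential decline.
- Terminal slope from the last 3, 4 or 6 points (48 h schedule) or the last 2 or 3 (24 h schedule). Table 8-8 does not state the number.

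**Profile:** C(t) = 100 x 2^(-t/T) + B.

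**One case by hand** (T = 8 h, B = 1 IU/dl, last 3 points):
- Drug level at 24, 30 and 48 h: 12.50, 7.43 and 1.56 IU/dl. With B: 13.50, 8.43 and 2.56.
- Natural logs: 2.603, 2.132 and 0.941.
- Mean time is 34 h, with deviations -10, -4 and 14; the sum of squares is 312.
- Slope = (-10 x 2.603 - 4 x 2.132 + 14 x 0.941) / 312 = -0.0685 per h.
- Half-life = 0.693 / 0.0685 = 10.1 h, against a true 8 h: +26%.

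**Half-life bias, 48 h schedule (3 / 4 / 6 terminal points)**

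| B (IU/dl) | T = 8 h | T = 10 h | T = 12 h |
|---|---|---|---|
| 1 | +26% / +18% / +14% | +14% / +10% / +8% | +9% / +7% / +5% |
| 0.5 | +14% / +10% / +7% | +7% / +5% / +4% | +5% / +3% / +3% |
| 0.2 | +6% / +4% / +3% | +3% / +2% / +2% | +2% / +1% / +1% |

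**Clearance, 48 h schedule, B = 1, 4 points.** The full Table 8-8 calculation gives 3.96 instead of 4.18 mL/h/kg at T = 8 h (-5%), and 2.71 instead of 2.82 at T = 12 h (-4%).

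**24 h schedule, B = 1.** Half-life is +2% to +4% and clearance about -3%.

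**Residual drug behaves differently.** Drug left from an earlier dose decays at the same rate as the new dose, so in a mono-exponential profile it does not bias half-life. With an equal dose 84 h earlier and T = 12 h, the residual is 100 x 2^(-7) = 0.78 IU/dl and clearance falls by 0.8%. Subtracting that value as a constant would bias half-life by -5.5%.

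**Visit 1 is not a clean endogenous value.** Table 8-1 requires 48 h washout at visit 1, against 72 (-6) h below 12 years or 96 (-12) h from 12 years before PK. A 25 IU/kg dose 48 h earlier leaves 50 x 2^(-6) = 0.8 IU/dl at T = 8 h, still within the eligibility limit. Suppose visit 1 reads 0.8 IU/dl when the true endogenous level is 0.3. Subtracting 0.8 removes 0.5 too much and biases half-life on the 48 h schedule by -8% to -15% at T = 8 h and by -3% to -5% at T = 12 h.

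**The case against.** The strongest reply is that the size is unknown and may be nothing. The documents give no distribution of endogenous FVIII, no assay limit, no half-life and no terminal-point rule. The +26% needs endogenous activity exactly at the ceiling, an 8 h half-life and a 3-point slope. If every PK patient is below the assay limit before dosing, a correction is never triggered. PK is secondary and descriptive, with no hypothesis or acceptance limit. All of this stands, and it limits the weight of the point. It does not remove the direction of the bias or the differing treatment within one table.

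A second reply is that correction can do harm, as the visit 1 example shows. This also stands. A reader might infer that conclusions should rest on corrected profiles, since recovery is already corrected. The documents do not support that step: no sample cleanly separates endogenous from residual activity, and section 8.5.2.3 defines recovery without subtraction.

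A reader might also infer that the unequal bias on the 48 h and 24 h schedules distorts a comparison between age groups. Protocol section 16.4.3 and the matching SAP text plan no age-group PK comparison, although other endpoints are explicitly presented by age group. Nor would baseline correction repair such a comparison for AUC or clearance. With no endogenous activity at all, the linear trapezoid on the sparse paediatric times overstates AUC by 14%, 9% and 6% at half-lives of 8, 10 and 12 h, against 4%, 3% and 2% on the 48 h schedule.

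**Conclusion.** The point holds as a minor improvement. Table 8-8 leaves AUC, clearance and half-life uncorrected although endogenous FVIII up to 1% is allowed. Where such activity exists, half-life is biased upward and clearance downward.

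At the ceiling, the 48 h schedule gives half-life +5% to +26% and clearance -4% to -5%; the 24 h schedule gives half-life +2% to +4% and clearance about -3%. These figures rest on a 100 IU/dl peak, mono-exponential decline, true half-lives of 8 to 12 h and the terminal-point choices shown. The bias shrinks with the endogenous level and is nil without it. The primary endpoint, the safety endpoints and the sample size are unaffected.

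**What to change.** In the SAP, under Pharmacokinetic endpoints:

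1. Add a pre-specified sensitivity analysis that derives AUC0-inf, clearance and half-life on baseline-corrected profiles when pre-dose FVIII is measurable. Report corrected and uncorrected geometric means side by side, and do not base conclusions on the corrected set alone.
2. Take as the constant endogenous level no more than the smaller of the visit 1 value and the pre-dose PK value. Treat any excess pre-dose activity as residual drug decaying at the patient's own rate.
3. Reconcile Table 8-8 and section 8.5.2.3 on whether incremental recovery is adjusted for the pre-dose value.

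The cost is SAP wording and a second run of the PK calculation; no new samples are needed. The downside is that correction is noisy near the assay limit, and it can still over-correct if the subtracted value contains residual drug. That is why both sets should be shown.
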